5.4. Analysis of RTI and LRTI

5.4.1. Analysis of RTI and LRTI planned in protocol

The primary analysis will be performed on the ES of subjects with a negative RSV exposure status (at screening based on in-stream baseline serological testing) in the pooled single dose RSV vaccine group, the pooled two dose RSV vaccine group, and the pooled comparator group separately for first and second RSV seasons and overall. A similar analysis will be performed on the entire ES. As primary analysis, the assessment of RSV infection will be performed using the quantitative RT-PCR according to standardized case definitions (see Table 6 of the SAP) based on the available WHO case definitions.

The number of RSV infections within each group and the maximum disease severity of the event will be tabulated. The rate (with 95% CI) of RSV-RTI and RSV-LRTI and infections progressing to hospitalization will be evaluated for each of the three pooled groups.

The rate of very severe RSV-LRTI among RSV infected infants with a negative RSV exposure status (at screening based on in-stream baseline serological testing) from first vaccination (Day 1) up to the end of the first RSV transmission season will be estimated as well as 95% one-sided lower CI.

The proportion and the relative risk of subjects with at least one RSV-associated RTI (with 95% CI) between each of two pooled RSV vaccine groups and the pooled control group will be calculated for both the cohort of subjects with a negative RSV exposure status (at screening based on in-stream baseline serological testing) on the ES and on the entire ES. The same descriptive analysis will be performed for subjects with at least one RSV-associated LRTI and those with at least one RSV-associated severe LRTI.

Descriptive analyses (mean, median, min, max) of viral load assessed by the quantitative RT-PCR (RSV-A/B) of all cases as listed in Table 6 of the SAP will be tabulated by case category. This analysis will also be done on the three pooled groups.

The incidence rate of all cases as listed in Table 6 of the SAP (with 95% CI) will be calculated by the three pooled groups. The same descriptive analysis will be performed for all cause LRTI and all cause severe LRTI. These will also be presented for each viral etiology identified by the multiplex PCR.

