6. ANALYSIS INTERPRETATION

For the occurrence of very severe RSV-LRTI among RSV infected infants with a negative RSV exposure status (at screening based on in-stream baseline serological testing) from first vaccination (Day 1) up to the end of the first RSV transmission season, if the upper boundary of the 95% one-sided lower CI of the rate is under 80%, it indicates that the very severe RSV-LRTI rate is less than that of the historic RSV-FI trials [Kim, 1969].

Comparative analyses will be exploratory and should be interpreted with caution considering that there is no adjustment for multiplicity and that group sizes are small for these comparisons.

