10.1.3.19. Statistical methodology

10.1.3.20. Exact confidence intervals around proportions

The exact confidence intervals around within-group proportions are derived using the method of Clopper and Pearson [Clopper, 1934].

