N= number of subjects with at least one RSV infection (symptomatic or asymptomatic)

n/% = number/percentage of subjects reporting at least one RSV hospitalization

95%CI= Exact 95% confidence interval; LL = lower limit, UL = upper limit

Template 41 Number and percentage of subjects reporting the RSV infection of different severity (based on WHO case definition) by number of events experienced between vaccination dose 1 up to end of <first, second> RSV season for pooled RSV 1D, RSV 2D and Comparator/Placebo group <Exposed Set, Exposed Set with negative RSV baseline status>

Characteristics	Categories	<Each group> N=xx				
		n	%	95% CI	LL	UL
RSV infection-symptomatic or asymptomatic*	0					
	1					
	2					
RSV-RTI	0					
	1					
RSV-LRTI	0					
	1					
	2					
RSV-Severe LRTI	0					
	1					
RSV-very severe LRTI	0					
	1					
All cause LRTI	0					
	1					
	2					
	3					
RSV hospitalization\$	0					
	1					
	2					
	3					

Short group label = long group label

N = number of subjects in each group

n = number of subjects in a given category

% = $100 * n / N$

LL, UL for percentage = Exact 95% Lower and Upper confidence limits

Please note – Single episode can be considered in multiple category depending on the symptom experienced

* Association to RSV based on central testing only for asymptomatic visit (no local test available)

\$Confirmed RSV infection and hospitalized for acute medical condition

Template 42 Number and percentage of RSV infections and associated disease severity (based on WHO case definition) and relative risk from vaccination dose 1 up to end of <first, second> RSV season for pooled RSV 1D, RSV 2D and Comparator/Placebo group <Exposed Set, Exposed Set with negative RSV baseline status>

Categories	<Each Group> N =		Relative risk (RSV1D vs Comparator/Placebo)				Relative risk (RSV2D vs Comparator/Placebo)			
			95% CI		95% CI				95% CI	
	n	%	LL	UL	Values	LL	UL	Values	LL	UL
RSV asymptomatic (Excluding RSV-RTI, LRTI, RSV-severe LRTI or RSV-very severe LRTI)										
RSV RTI (Excluding LRTI, RSV-severe or very severe LRTI)										
RSV LRTI (Excluding RSV-severe or very severe LRTI)										
RSV-severe LRTI (Excluding RSV-very severe LRTI)										
RSV-very severe LRTI										

Short group label = long group label

* Association to RSV based on central testing only for asymptomatic visit (no local test available)

N = number of RSV positive samples in each group

n** = number of cases in each category

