RSV-ve = Subject are RSV negative at baseline

Template 56 Summary of subjects by unsolicited adverse event category with onset within 30 days of first and second vaccination (Exposed Set)

	<Group 1> N=XXXX				<Group 2> N=XXXX			
			95% CI				95% CI	
	n	%	LL	UL	n	%	LL	UL
At least one unsolicited adverse event	xxx	xx.x	xx.x	xx.x	xxx	xx.x	xx.x	xx.x
At least one related unsolicited adverse event	xxx	xx.x	xx.x	xx.x	xxx	xx.x	xx.x	xx.x
At least one grade 3 unsolicited adverse event	xxx	xx.x	xx.x	xx.x	xxx	xx.x	xx.x	xx.x
At least one grade 3 related unsolicited adverse event	xxx	xx.x	xx.x	xx.x	xxx	xx.x	xx.x	xx.x
At least one medically attended unsolicited adverse event	xxx	xx.x	xx.x	xx.x	xxx	xx.x	xx.x	xx.x

Any adverse event = at least one adverse event experienced (regardless of the MedDRA Preferred Term)

N = number of subjects with at least one administered vaccination

n/% = number/percentage of subjects reporting the adverse event at least once

95% CI = exact 95% confidence interval; LL = Lower Limit, UL = Upper Limit

Template 57 Number and percentage of subjects with at least one RSV-RTI progressing to RSV-LRTI, RSV-severe LRTI, RSV-very severe LRTI and RSV hospitalization from vaccination dose 1 up to end of <first, second> RSV season for pooled RSV 1D, RSV 2D and Comparator/Placebo groups <ES, Exposed Set with negative RSV exposure status>

Categories	<each group> N =				Total N =			
			90% CI				90% CI	
	n	%	LL	UL	n	%	LL	UL
RSV-LRTI								
RSV-severe LRTI								
RSV-very severe LRTI								
RSV hospitalization*								

<Blinded = Blinded group>

<RSV 1D = Pooled 1D RSV>

<RSV 2D = Pooled 2D RSV>

<COMP_PLB = Pooled comparator or placebo>

* Confirmed RSV infection and hospitalized for acute medical condition

N = number of subjects with at least one RSV-RTI infection

n/%= number/percentage of subjects reporting at least once the symptom

90%CI= Exact 90% confidence interval; LL = lower limit, UL = upper limit

Please note – Single episode is considered in single category of highest severity based on the symptom experienced

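### Template 57 puts exact 90% intervals on its RSV-LRTI, severe RSV-LRTI and hospitalization rows, where SAP section 5.4.1 plans 95%, and no text explains the change

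*SAP*

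**What the plan says.** Section 5.4.1 sets the level for the respiratory endpoints in three places.

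- For RSV-RTI, RSV-LRTI and progression to hospitalization: "The rate (with 95% CI) of RSV-RTI and RSV-LRTI and infections progressing to hospitalization will be evaluated for each of the three pooled groups".
- For every case type in Table 6, which includes severe RSV-LRTI and RSV hospitalization: "The incidence rate of all cases as listed in Table 6 of the SAP (with 95% CI) will be calculated by the three pooled groups".
- For very severe RSV-LRTI among RSV-infected infants with a negative RSV exposure status, up to the end of the first season, the rate "will be estimated as well as 95% one-sided lower CI".

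Section 6 attaches the SAP's only threshold to that last quantity. The rate is read as lower than in the historical formalin-inactivated vaccine trials "if the upper boundary of the 95% one-sided lower CI of the rate is under 80" per cent.

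Template 57 in section 13 has four rows: RSV-LRTI, severe RSV-LRTI, very severe RSV-LRTI and RSV hospitalization. Its denominator is given as "N = number of subjects with at least one RSV-RTI infection". The column headers show a 90% CI with lower and upper limits, and the footnote repeats it: "90%CI= Exact 90% confidence interval; LL = lower limit, UL = upper limit". The title offers both seasons and both the Exposed Set and its negative-exposure subset. Templates 39, 40 and 43 carry the footnote "95%CI= Exact 95% confidence interval; LL = lower limit, UL = upper limit".

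**The concern.** No section of the SAP text plans a 90% interval, and section 8 (changes from planned analyses) lists no such change. The level stands in both the headers and the footnote of Template 57, so it is unlikely to be a slip in one cell. A programmer who follows the template departs from section 5.4.1 for three of the four rows.

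Progression from RSV-RTI to lower-tract disease and hospitalization bears on the question of enhanced disease. With target pooled groups of 50 infants, and only the infected ones in the denominator, much of the information lies in the upper limit. A reader who sees hospitalization at 95% in Template 40 and at 90% in Template 57, on related denominators, could take a difference in confidence level for a difference in precision.

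**Working it through.** The SAP has no figure of its own to reproduce here. The check compares confidence levels and then measures the difference.

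**Step 1: level by row.**

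| Template 57 row | Level in the text | Level in Template 57 |
|---|---|---|
| RSV-LRTI | 95% (5.4.1) | exact 90%, both limits |
| Severe RSV-LRTI | 95% (5.4.1, through Table 6) | exact 90%, both limits |
| Very severe RSV-LRTI, first season, negative exposure status | one-sided 95% (5.4.1, 6) | exact 90%, both limits |
| RSV hospitalization | 95% (5.4.1) | exact 90%, both limits |

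Section 5.4.1 gives no sidedness for its ordinary 95% intervals, so they are read as two-sided.

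**Step 2: method.** Section 10.1.3.20 states: "The exact confidence intervals around within-group proportions are derived using the method of Clopper and Pearson". For x events in n subjects at two-sided level 1 − α:

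- lower limit = the α/2 quantile of Beta(x, n − x + 1), or 0 if x = 0
- upper limit = the 1 − α/2 quantile of Beta(x + 1, n − x)

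The planned level is α = 0.05. Template 57 uses α = 0.10.

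**Step 3: the three rows planned at 95%.** The SAP gives no expected number of infants with RSV-RTI, so the counts are assumptions.

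| x/n (assumed) | Exact 95% | Exact 90% | Fall in upper limit |
|---|---|---|---|
| 3/15 | 4.3 to 48.1% | 5.7 to 44.0% | 48.1 − 44.0 = 4.1 points |
| 5/20 | 8.7 to 49.1% | 10.4 to 45.6% | 49.1 − 45.6 = 3.5 points |
| 2/10 | 2.5 to 55.6% | 3.7 to 50.7% | 55.6 − 50.7 = 4.9 points |

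Over assumed denominators from 5 to 50 and a range of event counts, the ratio of the 90% width to the 95% width runs from about 0.82 to 0.92. The 90% interval is therefore about 8 to 18% narrower.

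**Step 4: the very severe row.** A one-sided 95% upper limit is the 0.95 quantile of Beta(x + 1, n − x). The upper end of a two-sided 90% interval uses 1 − 0.10/2 = 0.95, so the two are identical for any x and n. With no events the limit has a closed form. At 0/20 the one-sided 95% limit and the 90% upper limit are both 1 − 0.05^(1/20) = 13.9%, while the two-sided 95% upper limit is 1 − 0.025^(1/20) = 16.8%.

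The distinction can matter near the threshold. At an assumed 5/10 the one-sided limit is 77.8%, below 80%, and the two-sided 95% upper limit is 81.3%, above it. On this row the bound behind the 90% level is the planned one and should be kept.

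**The case against.** The best defence is that the 90% level was chosen on purpose to deliver the one-sided bound of sections 5.4.1 and 6. For very severe RSV-LRTI in the first season and the negative-exposure set, that stands. A reader might infer that every row of Template 57 is too narrow, or that the 80% criterion is compromised. The documents do not support either, because the upper limit on that row is the planned bound. The defence does not reach the other three rows, for which no one-sided limit is planned, and the template nowhere labels its upper limit as one-sided.

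A second defence is that nothing planned is lost. Template 39 gives RSV-LRTI, severe RSV-LRTI and hospitalization with exact 95% intervals over all subjects. Template 40 gives hospitalization among infected subjects, and Template 43 gives infections requiring hospitalization, also at 95%. This stands too. One can add that section 5.4.1 does not explicitly ask for RSV-LRTI or severe RSV-LRTI over infants with an RSV-RTI, so Template 57 is a conditional version of the planned rates. But the text gives this conditional table no different level, and 95% is the only two-sided level it states for these outcomes.

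A reader might also infer that the narrower intervals understate the risk of progression. That is too strong. The level is printed in both header and footnote, a correctly labelled 90% interval is valid at its own level, and no decision rule attaches to these three rows.

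**Conclusion.** The inconsistency is real and limited. Three descriptive rows of Template 57 (RSV-LRTI, severe RSV-LRTI and hospitalization) carry intervals below the 95% level of section 5.4.1 and out of step with Templates 39, 40 and 43, for both seasons and both analysis sets, with no supporting text. The upper limit is about 3 to 5 points lower at the counts tabulated above. Those counts are assumed, but the direction is not: at the same data a 90% exact interval is always narrower than a 95% one. The very severe row for the first season and negative-exposure set is right for its criterion and only unlabelled. No threshold or stated conclusion changes.

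**What to change.** In Template 57, replace the exact 90% intervals with exact two-sided 95% intervals on the RSV-LRTI, severe RSV-LRTI and hospitalization rows. For very severe RSV-LRTI in the first season and negative-exposure set, show the one-sided 95% upper limit in its own labelled column, with a footnote pointing to the criterion in section 6. For the very severe row in the other season and set combinations, where no one-sided limit is planned, state which level applies.

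If the team prefers to keep 90% throughout, section 5.4.1 should say so and give the reason. That closes the gap in the text but leaves Template 57 at a different level from Templates 39, 40 and 43, so the first option is better.

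The cost is a header, a footnote and one column. No new data or analysis is needed, and the three intervals become slightly wider.

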9.2. RTI and LRTI

During the analysis of the study, all cases identified during the surveillance of RSV-RTI will be definitively classified as either RTI, LRTI, severe LRTI or very severe LRTI according to the standardized case definitions (Table 6 in the SAP) based on the available World Health Organization (WHO) case definitions (Table 6 in the protocol)

Table 6 Case definitions for data analysis

Case	At sea level up to 2500 meters elevation	Above 2500 meters elevation
RSV-RTI	Runny nose OR blocked nose OR cough AND Confirmed RSV infection ⁴	Same
RSV-LRTI	History of cough OR difficulty breathing ¹ AND SpO ₂ < 95% ² , OR RR increase ³ AND Confirmed RSV infection ⁴	Same but with SpO₂ < 92%
severe RSV-LRTI	Meeting the case definition of RSV-LRTI AND SpO ₂ < 93% ² , OR lower chest wall in-drawing	Same but with SpO₂ < 90%
very severe RSV-LRTI	Meeting the case definition of RSV-LRTI AND SpO ₂ < 90% ² , OR inability to feed, OR failure to respond / unconscious	Same but with SpO₂ < 88%

Case	At sea level up to 2500 meters elevation	Above 2500 meters elevation
RSV hospitalization	Confirmed RSV infection ⁵ AND Hospitalized for acute medical condition ⁶	Same
All-cause LRTI	History of cough OR difficulty breathing ¹ AND SpO ₂ < 95% ² , OR RR increase ³	Same but with SpO₂ <92%

LRTI = lower respiratory tract infections; RR = respiratory rate; RTI = respiratory tract infections; SpO₂ = blood oxygen saturation.

¹ Based on history reported by parents.

² The lowest value during the course of illness will be used.

³ RR increase defined as:≥ 50/minute (2 to 11 months of age) ; ≥ 40/minute (12 months of age or above) ;
The highest value during the course of the illness will be used.

⁴ RSV infection confirmed on nasal swab positive for RSV A or B by quantitative Reverse Transcription Polymerase Chain Reaction (qRT-PCR).

⁵ RSV sampling and testing is based on medical judgment of medical practitioner or driven by algorithm.

⁶ Hospitalization is defined as a medical decision that the infant requires admission for observation or treatment.

- For the analysis of RTI episode, a new RTI episode will be defined as any occurrence of cough, runny nose, blocked nose, wheezing or difficulty breathing with an interval of at least 7 symptom free days since the last episode of RTI that was diagnosed.
- For molecular biology (qRT-PCR test), the following cut-off will be applied: -

System	Component	Method	Unit	Cut-off

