Template 49 Listing of RSV-RTI requiring hospitalization and type of inpatient facility required from vaccination dose 1 up to end of second RSV season <Exposed Set, Exposed Set with negative RSV baseline status>

Group	Sub No.	Sex	Age at episode (month)	Country	Classification of episode per WHO*	Total days hospitalized	No. of days of monitoring or nursing	No. of days of strict or intravenous fluids given	No. of days oxygen administered	No. of days respiratory support given	No. of days mechanical ventilation given	No. of days child kept in hospital	No. of days in paediatrics intensive care unit	RVP	Pathogen identified in RVP
														Yes/No	

Short group label = long group label

*subject will be classified per maximum severity experienced

Template 50 Number and percentage of subjects with highest associated severity of RSV infection (based on WHO case definition) from vaccination dose 1 up to <first, second> RSV season for pooled RSV 1D, RSV 2D and Comparator/Placebo groups <Exposed Set, Exposed Set with negative RSV baseline status>

Categories	Group N =				Total N =			
	n**	n	%	95% CI	n**	n	%	95% CI
No Infection								
RSV asymptomatic (Excluding RSV-RTI, RSV-LRTI, RSV-severe LRTI or RSV-very severe LRTI)								
RSV RTI (Excluding RSV-LRTI, RSV-severe or very severe LRTI)								
RSV LRTI (Excluding RSV-severe or very severe LRTI)								
RSV-severe LRTI (Excluding RSV-very severe LRTI)								
RSV-very severe LRTI								

Short group label = long group label

N = number of subjects in each group

n** = number of cases in each category

n/% = number/percentage of subjects reporting at least once the case

95%CI= Exact 95% confidence interval; LL = lower limit, UL = upper limit

Please note – Single episode can be considered in single category depending on the highest severity symptom experienced

Template 51 Number and percentage of subjects reporting the RSV infection of maximum severity (based on WHO case definition) by number of events experienced between vaccination dose 1 up to end of <first, second> RSV season for pooled RSV 1D, RSV 2D and Comparator/Placebo groups <Exposed Set, Exposed Set with negative RSV baseline status >

Characteristics	Categories	Total			95% CI	
		N	n	%	LL	UL
RSV asymptomatic (Excluding RSV-RTI, RSV-LRTI, RSV-severe LRTI or RSV-very severe LRTI)	0					
	1					
	2					
RSV-RTI (Excluding RSV-LRTI, RSV severe or very severe LRTI)	0					
	1					
RSV-LRTI (Excluding RSV severe or very severe LRTI)	0					
	1					

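### Template 57 is defined as progression from RSV-RTI, but its counting note drops the most severe infants from the RSV-LRTI and severe rows, so those two rows are understated

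*SAP*

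**What the plan says.** The title of Template 57 (SAP section 13) is "Number and percentage of subjects with at least one RSV-RTI progressing to RSV-LRTI, RSV-severe LRTI, RSV-very severe LRTI and RSV hospitalization". The denominator is "N = number of subjects with at least one RSV-RTI infection", and n is defined as "number/percentage of subjects reporting at least once the symptom". The rows are labelled simply RSV-LRTI, RSV-severe LRTI, RSV-very severe LRTI and RSV hospitalization, and the intervals are exact 90% intervals. The last note under the table reads "Single episode is considered in single category of highest severity based on the symptom experienced".

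Table 6 (SAP section 9.2) defines both severe and very severe RSV-LRTI as "Meeting the case definition of RSV-LRTI" plus a further criterion. RSV hospitalization is a separate case type there and not a step on the severity scale.

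The neighbouring templates handle the choice differently:

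- Templates 42, 44, 45, 50 and 51 use exclusive categories and say so in the row labels, for example "RSV LRTI (Excluding RSV-severe or very severe LRTI".
- Template 41 uses plain labels and lets one episode count in several rows.
- Templates 44 and 45 exempt hospitalization from the single-category rule. Template 57 has a hospitalization row and no such exemption.

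**The concern.** The title, the labels and the definition of n describe one quantity, and the note produces another. An infant whose RSV-RTI became a severe LRTI has progressed to LRTI under Table 6, yet the note leaves that infant out of the RSV-LRTI row. Nothing in the row label warns the reader.

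This table is where it matters. The SAP plans blood sampling for potential enhanced disease and, in section 6, compares very severe RSV-LRTI with historic vaccine trials. Template 57 is the only template that gives progression to LRTI over subjects with an RSV-RTI, with an interval. If more infants in a vaccine group moved from LRTI to severe LRTI, the printed RSV-LRTI proportion for that group would fall. Read alone, that row could be taken as a benefit.

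**Working it through.** The SAP gives no progression rates, so there is no figure of its own to reproduce. The counts below are assumptions that only show what the note does. Each infant has one episode.

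**Formulas.** Let a, b and c be the infants whose episode peaks at LRTI, severe and very severe, out of N with an RSV-RTI.

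- Under the note: LRTI row = a/N, severe row = b/N, very severe row = c/N.
- Under Table 6: LRTI = (a+b+c)/N, severe or worse = (b+c)/N, very severe = c/N.
- Exact 90% interval for x of N (Clopper-Pearson): lower limit is the 5% quantile of Beta(x, N−x+1); upper limit is the 95% quantile of Beta(x+1, N−x).

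**One group, N = 20, a = 4, b = 3, c = 1.**

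| Row | Under Table 6 | Printed under the note |
|---|---|---|
| RSV-LRTI | 8/20 = 40% (21.7–60.6) | 4/20 = 20% (7.1–40.1) |
| Severe | 4/20 = 20% (7.1–40.1) | 3/20 = 15% (4.2–34.4) |
| Very severe | 1/20 = 5% (0.3–21.6) | same |

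**Two groups, N = 20 each.** Comparator a, b, c = 6, 1, 0; vaccine = 2, 4, 3.

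| Row | Comparator, Table 6 | Vaccine, Table 6 | Comparator, printed | Vaccine, printed |
|---|---|---|---|---|
| RSV-LRTI | 7/20 = 35% (17.7–55.8) | 9/20 = 45% (25.9–65.3) | 6/20 = 30% (14.0–50.8) | 2/20 = 10% (1.8–28.3) |
| Severe | 1/20 = 5% (0.3–21.6) | 7/20 = 35% (17.7–55.8) | 1/20 = 5% (0.3–21.6) | 4/20 = 20% (7.1–40.1) |
| Very severe | 0/20 = 0% (0–13.9) | 3/20 = 15% (4.2–34.4) | same | same |

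In the RSV-LRTI row the order of the groups reverses. In the severe row the order holds here but the gap shrinks from 30 to 15 percentage points. The severe row can reverse too: with b, c = 3, 0 against 1, 4, severe or worse is 3/20 = 15% against 5/20 = 25%, while the printed row is 15% against 1/20 = 5%.

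**Range.** If 40% of RSV-RTI infants reach LRTI and a share f of those go on to severe or very severe disease, the printed row is 40% × (1−f). For f = 0, 25, 50, 75 and 100% that gives 40, 30, 20, 10 and 0%, whatever N is.

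**Several episodes.** The note ranks episodes, while n counts subjects. An infant with one episode peaking at LRTI and another at severe appears in both rows. An infant is lost from the RSV-LRTI row only if every LRTI episode peaked higher, and from the severe row only if every severe-or-worse episode peaked at very severe.

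**The case against.** The strongest reply is that nothing is hidden. An infant who leaves the RSV-LRTI row appears in a row below it. The very severe row has no severity level above it, so the ranking does not reduce it, and the criterion in section 6 concerns very severe RSV-LRTI only. With one episode per infant, the three severity rows add up to cumulative progression. Template 39 lists subjects with RSV-RTI and with each LRTI level, without an exclusive-category note, so a rough ratio could be formed. Comparative analyses are exploratory, and section 5.4.1 sets no exclusive rule for progression.

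Most of this stands, and it limits the point. A reader might infer that Template 57 makes worse disease look like less progression overall, or that its rows are mutually exclusive for subjects. The documents support neither: the shift shows lower in the table, and exclusivity is per episode.

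It does not rescue the two affected rows. Sums of rows carry no printed interval, and with repeat episodes they can count an infant twice. The Template 39 denominator is all vaccinated subjects. The ratio of its LRTI to RTI counts is only approximate, because Table 6 allows an RSV-LRTI through difficulty breathing without RTI symptoms, and it has no interval either. Template 40 covers hospitalization alone.

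On hospitalization, the natural reading is that a severity ranking leaves that row alone. The missing exemption is a drafting gap. Taken literally, though, the note would make hospitalization compete with the severity rows.

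**Conclusion.** The point holds in a limited form. Template 57 contradicts itself: the note cannot stand together with the title, the plain labels and the definition of n, given the nested definitions in Table 6. If the note is followed, the RSV-LRTI and severe rows are understated whenever any infant's qualifying episodes all peak at a higher level, and the direction between groups can reverse in either row.

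The size depends on how many infants progress further, which the SAP does not state. In the one-group illustration the RSV-LRTI row is halved, from 40% to 20%; over the range shown, the loss runs from nothing to the whole row. The figures assume one episode per infant and invented counts.

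This should be corrected before the table is programmed. It does not affect the section 6 criterion, provided hospitalization is not treated as a category ranked above very severe LRTI.

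**What to change.** Replace the closing note of Template 57 with: *Rows are cumulative: a subject counts in every category whose Table 6 definition is met by at least one episode; RSV hospitalization is counted independently of severity.* The note then agrees with the title, the definition of n and Table 6.

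If an exclusive breakdown over RSV-RTI subjects is also wanted, add it as separate rows whose labels state the exclusion, as the sister templates do. Template 50 cannot stand in for it, because its denominator is all subjects in the group. Keeping exclusive rows with such labels and adding a row for any RSV-LRTI would also remove the mislabelling, but cumulative severe-or-worse progression would then need its own row as well.

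The cost is one footnote, one programming flag and possibly a few extra rows. No new data are needed.
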